1.2.3 Clinical Pharmacokinetics

Twelve Phase I, five Phase II, and two Phase III clinical studies were conducted to explore the clinical pharmacology of ruxolitinib in healthy volunteers and in patients with MF, ET, PV, subjects with renal or hepatic impairment, prostate cancer, MM or rheumatoid arthritis (RA).

- Oral absorption of ruxolitinib is rapid and nearly complete, with $\geq 95\%$ absorption indicating high in vivo permeability in the human gastrointestinal tract, consistent with a Biopharmaceutical Classification System (BCS) Class I compound. Mean peak plasma concentrations (C_{max}) is achieved 1-2 h post-dose.
- The effect of food on ruxolitinib exposure is minimal and is not expected to be clinically significant; as a result, the drug may be administered either with or without food.
- Dose proportional exposure is observed between 5 and 200 mg dose range with linear pharmacokinetics (PK).
- Plasma protein binding is approximately 97% in vitro. There is moderate distribution to organs and tissues with no long-term retention of drug-related material in preclinical species and limited drug penetration into the central nervous system (CNS) or across the blood-brain barrier.
- There is $>95\%$ [¹⁴C] drug recovery in a mass balance study with 74% and 22% of the dose excreted in urine and feces of healthy subjects, respectively. Less than 1% of the administered dose is recovered in urine and feces as unchanged parent drug.
- The mean terminal elimination half-life is ~ 3 h with no appreciable accumulation of either parent or metabolites with twice daily dosing.
- Metabolism is predominantly via the cytochrome P450 isozyme CYP3A4 to yield oxygenated and subsequent conjugated metabolites.
- Oxidative metabolites of ruxolitinib retain pharmacological activity albeit with one half to one fifth of the activity of the parent compound. Ex vivo pharmacokinetic/pharmacodynamic (PK/PD) analysis indicates that the sum total of 8 active metabolites contribute to 18% of the overall PD activity of ruxolitinib.
- When administering ruxolitinib with strong CYP3A4 inhibitors, the total daily dose should be reduced by approximately 50%.
- No dose adjustment is necessary when co-administering ruxolitinib with strong CYP3A4 inducers.

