- In patients with severe [creatinine clearance (Cl_{cr}) < 30 mL/min] and moderate renal impairment ($Cl_{cr} = 30 - 49$ mL/min), the recommended starting dose based on platelet count should be reduced by approximately 50% to be administered twice a day. Patients on hemodialysis should initiate ruxolitinib with a single dose of 15 mg or 20 mg based on platelet counts with subsequent single doses only on hemodialysis days and following each hemodialysis session. Ruxolitinib doses should be titrated based on individual safety and efficacy.
- In patients with mild, moderate or severe hepatic impairment, the recommended starting dose based on platelet count should be reduced by approximately 50% with subsequent dose titration based on individual safety and efficacy.

- Baseline elevations in inflammatory markers such as tumor necrosis factor alpha (TNF α), interleukin (IL)-6, and C-reactive protein (CRP) noted in subjects with MF were associated with constitutional symptoms such as fatigue, pruritus, and night sweats. Decreases were observed in these markers over the 24 weeks of treatment with ruxolitinib, with no evidence that subjects became refractory to the effects of ruxolitinib treatment.

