Both pre-clinical and clinical data highlight the central role of proinflammatory cytokines, particularly IFN- γ , that are dependent upon the JAK/STAT signaling in HPS pathogenesis.²⁷⁻³¹ The disease biology and clinical manifestations associated with HPS are driven by this underlying “cytokine storm”, culminating in T-cell accumulation and macrophage activation. Therefore, inhibition of JAK/STAT signaling may represent a novel therapeutic approach. As ruxolitinib inhibits upstream Janus kinases (JAK) at nanomolar concentrations, and is well tolerated in myelofibrosis patients (and alleviates signs/symptoms associated with hypercytokinemia), we sought to determine whether it inhibits STAT1 phosphorylation in IFN- γ treated macrophages. Not surprisingly, ruxolitinib (1 μ M) was able to inhibit STAT1 phosphorylation in treated macrophages. Therefore, ruxolitinib represents a novel therapeutic

approach for secondary HPS that has the potential to dramatically change the standard of care (and improve outcomes) for these patients. Cytopenias (including thrombocytopenia) observed in HPS are secondary to consumption (“hemophagocytosis”) and cytokine-mediated suppression, and are not secondary to underlying bone marrow “failure”. Therefore, treatment will be initiated at 15 mg po twice daily.

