6.2 General Concomitant Medications and Supportive Care Guidelines

Because there is a potential for interaction of Ruxolitinib with other concomitantly administered drugs through the cytochrome P450 system, the case report form must capture the concurrent use of all other drugs, over-the-counter medications, or alternative therapies. The Principal Investigator should be alerted if the patient is taking any agent known to affect CYP3A4. In patients who concurrently take strong CYP3A4 inhibitors and a platelet count of at least 50,000 the dose of ruxolitinib should be capped at 10 mg twice daily due to the concern for increased serum concentrations of ruxolitinib's active metabolites. Strong CYP3A4 inhibitors, including grapefruit juice, should be avoided whenever possible.

Patients should receive full supportive care, including transfusions of blood and blood products, cytokines, antibiotics, anti-emetics, etc when appropriate.

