7. DOSING DELAYS / DOSE MODIFICATIONS

Ruxolitinib will be dosed twice daily throughout the study. In the event a dose is missed, the subject should be instructed to take the next scheduled dose.

Dose Level	Ruxolitinib (BID schedule)	
	CrCl \geq 60	CrCl 15-59
Level 1 (starting dose)	15 mg	10 mg
Level -1 (reduction)	10 mg	5 mg
Level -2 (reduction)	5 mg	Hold

Event Name	Nausea
Grade of Event	Management/Next Dose for Ruxolitinib
\leq Grade 1	No change in dose
Grade 2	Hold until \leq Grade 1. Resume at same dose level.
Grade 3	Hold* until $<$ Grade 2. Resume at one dose level lower, if indicated.**
Grade 4	Off protocol therapy
*Patients requiring a delay of $>$ 4 weeks should go off protocol therapy.	
**Patients requiring $>$ two dose reductions should go off protocol therapy.	
Recommended management: antiemetics.	

Event Name	Vomiting
Grade of Event	Management/Next Dose for Ruxolitinib
\leq Grade 1	No change in dose
Grade 2	Hold until \leq Grade 1. Resume at same dose level.
Grade 3	Hold* until $<$ Grade 2. Resume at one dose level lower, if indicated.**
Grade 4	Off protocol therapy
*Patients requiring a delay of $>$ 4 weeks should go off protocol therapy.	
**Patients requiring $>$ two dose reductions should go off protocol therapy.	
Recommended management: antiemetics; in the event a dose of ruxolitinib is vomited, it is recommended that subjects resume ruxolitinib with the next scheduled dose.	

Event Name	Diarrhea
Grade of Event	Management/Next Dose for Ruxolitinib
≤ Grade 1	No change in dose
Grade 2	Hold until ≤ Grade 1. Resume at same dose level.
Grade 3	Hold* until < Grade 2. Resume at one dose level lower, if indicated. **
Grade 4	Off protocol therapy
*Patients requiring a delay of >4 weeks should go off protocol therapy. **Patients requiring > two dose reductions should go off protocol therapy.	
Recommended management: Loperamide antidiarrheal therapy Dosage schedule: 4 mg at first onset, followed by 2 mg with each loose motion until diarrhea-free for 12 hours (maximum dosage: 16 mg/24 hours) Adjunct anti-diarrheal therapy is permitted and should be recorded when used.	

Event Name	Thrombocytopenia
Platelet Count	Management/Next Dose for Ruxolitinib
50,000-100,000	Level 1 Ruxolitinib
35,000-49,999	Level -1 (reduction) if determined to be secondary to Ruxolitinib per the discretion of the investigator or PI.
20,000-34,999	Level -2 (reduction)

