Less than 20,000	Hold* until platelet count is at least 50,000 then resume at one dose level lower if determined to be secondary to Ruxolitinib per the discretion of the investigator or PI. Transfuse as needed for bleeds.
*Patients requiring a delay of >4 weeks should go off protocol therapy. **Patients requiring > two dose reductions should go off protocol therapy.	

Treatment will be discontinued for any patient that experiences a Grade 4 non-hematologic toxicity that is possibly related to ruxolitinib.

Dose adjustments for grades 1-3 non-hematologic toxicity that is possibly related to ruxolitinib will be at the discretion of the investigator or PI.

With the exception of thrombocytopenia (see table above), dose adjustments for grades 1-4 hematologic toxicity that is possibly related to ruxolitinib will be at the discretion of the investigator or PI.

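### The strong CYP3A4 inhibitor cap in Section 6.2 lapses below 50,000 platelets, so at CrCl >=60 a disease-related count of 35,000-49,999 defaults to a higher dose than a safer count

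*Combined protocol and SAP*

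**What the plan says.** Section 6.2 addresses patients who take a strong CYP3A4 inhibitor and have "a platelet count of at least 50,000 the dose of ruxolitinib should be capped at 10 mg twice daily". It explains the cap by a concern about higher serum concentrations of active drug material. It also asks that the Principal Investigator be told of any agent affecting CYP3A4, and advises against strong inhibitors where there is a choice. It gives no inhibitor dose for counts below 50,000.

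Section 7 sets Level 1 at 15 mg twice daily for creatinine clearance (CrCl) of 60 or more, and at 10 mg for CrCl 15-59. Its thrombocytopenia table keeps Level 1 at 50,000-100,000. At 35,000-49,999 the instruction is "Level -1 (reduction) if determined to be secondary to Ruxolitinib per the discretion of the investigator or PI". At 20,000-34,999 it is Level -2 with no attribution condition, and below 20,000 the drug is held.

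Section 1.3 explains why low counts do not lower the starting dose: "Cytopenias (including thrombocytopenia) observed in HPS are secondary to consumption" and cytokine-mediated suppression, not marrow failure. It concludes: "Therefore, treatment will be initiated at 15 mg po twice daily". Sections 4.1 and 4.2 set no lower platelet limit for entry.

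The pharmacokinetic background in Section 1.2.3 adds a general statement with no platelet condition: "When administering ruxolitinib with strong CYP3A4 inhibitors, the total daily dose should be reduced by approximately 50" percent.

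**The concern.** The cap protects against excess exposure caused by the inhibitor, and that exposure is the same problem at 40,000 platelets as at 60,000. Because the cap is conditional on the higher count, the protection lapses for the patient with less platelet reserve. Section 7 fills the gap only when the low count is blamed on ruxolitinib. A count that was low before the first dose cannot be, and Section 1.3 says that disease-related low counts are expected in this population.

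At stake is one cell of the dosing rules. A site following the text as written would give the patient with fewer platelets more of a drug that the protocol itself associates with thrombocytopenia, together with an agent that raises its concentration.

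**Working it through.** No power or error-rate formula bears on this. The check applies the two operative rules together.

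**Inputs**
- Level 1, -1 and -2 at CrCl >=60: 15, 10 and 5 mg twice daily (Section 7).
- Level 1, -1 and -2 at CrCl 15-59: 10 mg, 5 mg and hold (Section 7).
- Platelet table and its attribution condition (Section 7).
- Inhibitor cap: 10 mg twice daily, at 50,000 or more only (Section 6.2).

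**Rule.** Dose = Section 7 dose for the count. If a strong inhibitor is taken and the count is 50,000 or more, dose = min(Section 7 dose, 10 mg).

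**Plan's own figure.** CrCl >=60, count 50,000 or more: min(15, 10) = 10 mg twice daily, which matches the stated cap.

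**Default dose with a strong inhibitor (mg twice daily)**

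| Platelets | CrCl >=60, attributed to drug | CrCl >=60, not attributed | CrCl 15-59, not attributed |
|---|---|---|---|
| 50,000 or more | 10 | 10 | 10 |
| 35,000-49,999 | 10 | **15** | 10 |
| 20,000-34,999 | 5 | 5 | hold |
| below 20,000 | hold | hold | hold |

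**Size.** 2 x 15 = 30 mg/day against 2 x 10 = 20 mg/day, and 30/20 = 1.5.

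The inversion appears in one cell only. If the count is attributed to ruxolitinib, Level -1 gives 10 mg and the dose does not rise. At CrCl 15-59, Level 1 is already 10 mg, so the cap does not bind and there is no inversion.

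**After the fix.** With the cap applied at any count, the unattributed CrCl >=60 column reads 10, 10, 5, hold. In the affected cell the dose goes from 30 to 20 mg/day, and the ratio to the patient at 50,000 or more is 20/20 = 1.0.

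**The case against.** The best reply is that silence is not an instruction. The investigator is told to alert the Principal Investigator, to avoid the inhibitor if possible, and is free to dose below a ceiling. Blood counts are taken at least every 72 hours in weeks 1-5 (Section 12.2), and Level -2 applies unconditionally once a count is 20,000-34,999. For a fall during treatment, attribution is a judgement: with an inhibitor raising exposure, the fall can reasonably be put down to ruxolitinib, which gives 10 mg and removes the inversion. All of this stands and limits the risk. None of it states a dose for an unattributed count of 35,000-49,999, and the attribution route is closed for a count that was low before the first dose.

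Section 1.3 could also be read as deliberate acceptance of full dosing in disease-related thrombocytopenia. That explains not reducing for platelets. It does not explain withdrawing a cap whose stated reason is drug concentration.

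Four stronger readings are tempting, and the documents do not support them.
- *The rules contradict the Section 7 platelet table.* They do not. For an unattributed count, Section 7 gives Level 1 both at 50,000-100,000 and at 35,000-49,999. The step comes from where the Section 6.2 cap stops.
- *The dose is a larger multiple of what Section 1.2.3 advises.* That section is background. Section 6.2 already departs from it with a cut of one third (1 - 20/30) where the background says about half. It is not a safe benchmark for the size of the error, nor does it supply the missing operative dose.
- *Patients with reduced renal function are also missed because the cap does not lower their 10 mg start.* Section 1.2.3 lists a renal reduction ("the recommended starting dose based on platelet count should be reduced by approximately 50% to be administered twice a day") separately from the inhibitor reduction, but nothing says that the two multiply. A ceiling that does not bind is not an error.
- *The 70% thrombocytopenia listed in Section 8.1.1 measures the harm.* It is not a rate in this disease. The oncology database in Section 8 is mostly myelofibrosis (679 of 787 patients), and Section 1.3 describes a different mechanism for low counts here.

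**Conclusion.** The concern holds as a narrow, minor safety correction. For CrCl >=60, platelets of 35,000-49,999 not attributed to ruxolitinib, and an unavoidable strong CYP3A4 inhibitor, the written default is 30 mg/day, 1.5 times the 20 mg/day allowed at a higher count.

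This assumes that where neither rule reduces the dose, Level 1 continues. It is firmest for a count already in the band before the first dose. It is weaker for a fall on treatment, where attribution is discretionary. The text also does not say whether a patient already capped at 10 mg goes back to 15 mg when the count drops below 50,000. The 1.5 ratio rests on Sections 6.2 and 7 alone.

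Reach is small: at most 10 patients, with no figure for how often strong inhibitors are used, so the number affected could be zero.

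**What to change.** In Section 6.2:
1. Delete the platelet condition, so that the 10 mg twice daily cap applies whenever a strong CYP3A4 inhibitor is given.
2. State that Section 7 governs where it gives a lower dose or a hold.
3. State that the cap does not count as a Section 7 dose reduction. Without this, it could be counted towards the limit of two reductions before protocol therapy ends, or change what one level lower means after a hold.

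The cost is a drop from 30 to 20 mg/day in the few patients affected, in a disease that Section 1.1 describes as always fatal without treatment. That is the dose Section 6.2 already imposes at 50,000 or more. The change creates no new hold, and sample size, primary endpoint and primary analysis are untouched.

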6.3 Duration of Follow Up

Patients will be followed for toxicity for 30 days after treatment has been discontinued or until death, whichever occurs first. Patients will be followed for survival for up to five years or until the end of the study or death, whichever occurs first.

The clinical course of each event will be followed until resolution, stabilization, or until it has been determined that the study treatment or participation is not the cause for a maximum of 6 months.

Serious adverse events that are still ongoing at the end of the study period will necessitate follow-up to determine the final outcome. Any serious adverse event that occurs after the study period and is considered to be possibly related to the study treatment or study participation will be recorded and reported immediately per IRB and FDA reporting guidelines.

7. DOSING DELAYS / DOSE MODIFICATIONS

Ruxolitinib will be dosed twice daily throughout the study. In the event a dose is missed, the subject should be instructed to take the next scheduled dose.

Dose Level	Ruxolitinib (BID schedule)	
	CrCl \geq 60	CrCl 15-59
Level 1 (starting dose)	15 mg	10 mg
Level -1 (reduction)	10 mg	5 mg
Level -2 (reduction)	5 mg	Hold

Event Name	Nausea
Grade of Event	Management/Next Dose for Ruxolitinib
\leq Grade 1	No change in dose
Grade 2	Hold until \leq Grade 1. Resume at same dose level.
Grade 3	Hold* until $<$ Grade 2. Resume at one dose level lower, if indicated.**
Grade 4	Off protocol therapy
*Patients requiring a delay of $>$ 4 weeks should go off protocol therapy.	
**Patients requiring $>$ two dose reductions should go off protocol therapy.	
Recommended management: antiemetics.	

Event Name	Vomiting
Grade of Event	Management/Next Dose for Ruxolitinib
\leq Grade 1	No change in dose
Grade 2	Hold until \leq Grade 1. Resume at same dose level.
Grade 3	Hold* until $<$ Grade 2. Resume at one dose level lower, if indicated.**
Grade 4	Off protocol therapy
*Patients requiring a delay of $>$ 4 weeks should go off protocol therapy.	
**Patients requiring $>$ two dose reductions should go off protocol therapy.	
Recommended management: antiemetics; in the event a dose of ruxolitinib is vomited, it is recommended that subjects resume ruxolitinib with the next scheduled dose.	

Event Name	Diarrhea
Grade of Event	Management/Next Dose for Ruxolitinib
≤ Grade 1	No change in dose
Grade 2	Hold until ≤ Grade 1. Resume at same dose level.
Grade 3	Hold* until < Grade 2. Resume at one dose level lower, if indicated. **
Grade 4	Off protocol therapy
*Patients requiring a delay of >4 weeks should go off protocol therapy. **Patients requiring > two dose reductions should go off protocol therapy.	
Recommended management: Loperamide antidiarrheal therapy Dosage schedule: 4 mg at first onset, followed by 2 mg with each loose motion until diarrhea-free for 12 hours (maximum dosage: 16 mg/24 hours) Adjunct anti-diarrheal therapy is permitted and should be recorded when used.	

Event Name	Thrombocytopenia
Platelet Count	Management/Next Dose for Ruxolitinib
50,000-100,000	Level 1 Ruxolitinib
35,000-49,999	Level -1 (reduction) if determined to be secondary to Ruxolitinib per the discretion of the investigator or PI.
20,000-34,999	Level -2 (reduction)
Less than 20,000	Hold* until platelet count is at least 50,000 then resume at one dose level lower if determined to be secondary to Ruxolitinib per the discretion of the investigator or PI. Transfuse as needed for bleeds.
*Patients requiring a delay of >4 weeks should go off protocol therapy. **Patients requiring > two dose reductions should go off protocol therapy.	

Treatment will be discontinued for any patient that experiences a Grade 4 non-hematologic toxicity that is possibly related to ruxolitinib.

Dose adjustments for grades 1-3 non-hematologic toxicity that is possibly related to ruxolitinib will be at the discretion of the investigator or PI.

With the exception of thrombocytopenia (see table above), dose adjustments for grades 1-4 hematologic toxicity that is possibly related to ruxolitinib will be at the discretion of the investigator or PI.

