4.1 Inclusion Criteria

Patients must meet all of the following inclusion criteria to be eligible for enrollment:

1. Patients, or their legally authorized representative, must voluntarily provide written IRB-approved informed consent.
2. Males and females, 18 years of age or older at the time of enrollment.
3. Patients must meet the diagnostic criteria for HPS (at least 5 of the following):
 - fever
 - splenomegaly
 - cytopenia involving ≥ 2 cell lines (Hemoglobin < 9 g/dL; platelets $< 100,000/\mu\text{L}$; absolute neutrophil count $< 1000/\mu\text{L}$)
 - hypertriglyceridemia or hypofibrinogenemia
 - tissue demonstration of hemophagocytosis
 - low or absent NK cell activity
 - serum ferritin ≥ 3000 ug/L
 - soluble IL-2 receptor (CD25) > 2400 U/mL.
4. In the investigator's opinion, the patient has the ability to participate fully in the study and comply with all its requirements.

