duration of exposure and follow-up, the types of TEAEs reported remained consistent with what was reported in the initial analysis. Thrombocytopenia/platelet count decrease remained the most frequently reported AE (58.1%). Anemia/Hgb decreased was reported in 84 subjects (54.2%), which was also an expected effect of ruxolitinib. Among the non-hematologic TEAEs, the most frequently reported TEAE was fatigue (44.5%) followed by diarrhea (35.5%), and peripheral edema (31.0%).

In the ruxolitinib-treated Phase III population, the overall frequency of AEs requiring dose reduction or interruption was 59.8%. This frequency was higher than in the control groups (placebo: 27.2%, BAT: 15.1%). The most frequently reported AEs requiring dose reduction or interruption in ruxolitinib-treated patients were thrombocytopenia (36.9%), platelet count decreased (7.6%) and anemia (5.6%). The high frequency for thrombocytopenia is due to protocol-mandated dose reductions and interruptions. Although there were no protocol-specified guidelines for dose reductions secondary to anemia, some investigators chose to reduce a patient's dose in the setting of anemia to minimize this particular effect of ruxolitinib. The frequency of these AEs was higher than in the control groups. All other AEs requiring dose reduction or interruption occurred with a frequency of 1.3% or less in the ruxolitinib-treated patients. For COMFORT-I at the Week 144 analysis for patients initially randomized to ruxolitinib 70 patients (45.2%) had at least 1 AE leading to interruption or discontinuation of study drug and 82 (52.9%) had at least 1 AE leading to dose reduction. Thrombocytopenia/platelet count decrease was the most common reason for dose reduction or discontinuation.

In the Phase III population, at the initial analysis, there were 34 deaths in total, 27 of which were on-treatment deaths: 20 deaths in study COMFORT-I (9 in the ruxolitinib group, 11 in the placebo group) and 7 deaths in study COMFORT-II (4 in the ruxolitinib group, 3 in the BAT group). The reasons for death (infections, intestinal perforation, disease progression and events probably due to disease progression, bleedings events) were similar in the ruxolitinib and the placebo groups.

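### With a strong CYP3A4 inhibitor and CrCl ≥60, the first platelet-triggered ruxolitinib reduction goes from 10 mg to 10 mg, and the 10 mg cap does not reach patients below 50,000 platelets

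*Combined protocol and SAP*

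**What the plan says.** Section 1.3 treats the cytopenias of this disease as disease-driven and sets the starting dose without regard to platelets: "Therefore, treatment will be initiated at 15 mg po twice daily". Section 4.1 counts "cytopenia involving ≥ 2 cell lines" among the diagnostic criteria, with platelets below 100,000 as one of the lines. Neither Section 4.1 nor Section 4.2 sets a lower platelet limit.

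On strong CYP3A4 inhibitors, Section 6.2 says that in patients who take one and have "a platelet count of at least 50,000 the dose of ruxolitinib should be capped at 10 mg twice daily". The reason given is higher levels of active metabolites. The section also asks that these inhibitors be avoided where possible and that the Principal Investigator be told of any agent affecting CYP3A4. The background in Section 1.2.3 has no platelet condition: "When administering ruxolitinib with strong CYP3A4 inhibitors, the total daily dose should be reduced by approximately 50" per cent.

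Section 7 defines fixed doses by renal function. For CrCl ≥60, Levels 1, -1 and -2 are 15, 10 and 5 mg twice daily. For CrCl 15-59 they are 10 mg, 5 mg and Hold. The thrombocytopenia table assigns "Level 1 Ruxolitinib" at 50,000-100,000. At 35,000-49,999 it assigns "Level -1 (reduction) if determined to be secondary to Ruxolitinib per the discretion of the investigator or PI". At 20,000-34,999 it assigns Level -2 with no attribution test, and below 20,000 it says "Hold* until platelet count is at least 50,000 then resume at one dose level lower" if the count is attributed to ruxolitinib. The investigator's general discretion over dose changes for hematologic toxicity expressly leaves out thrombocytopenia.

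**The concern.** The cap and the reduction table do not refer to each other. For CrCl ≥60, the capped dose and Level -1 are the same number, so the first attributed reduction changes nothing in the patients whose exposure the cap was meant to restrain. Separately, the cap's stated reason is pharmacokinetic and does not depend on platelets, yet the cap is conditional on them. As worded, a lower starting count can go with a higher dose.

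What is at stake is bleeding safety in a small subgroup. Section 8.1 names thrombocytopenia as the adverse event that most often led to dose reduction or interruption in the Phase III myelofibrosis population. The trial has up to 10 patients, and its efficacy test is a count of survivors that does not depend on these rules.

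**Working it through.** The plan gives no figure of its own to reproduce here. The check traces the dose through the written rules, using the levels and platelet bands in Section 7 and the cap in Section 6.2.

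**Step 1: first attributed fall to 35,000-49,999, starting from 50,000 or above.** On a strong inhibitor, the starting dose is the smaller of Level 1 and 10 mg.

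| Patient | Dose before (mg twice daily) | Dose ordered | Change |
|---|---|---|---|
| CrCl ≥60, no inhibitor | 15 | 10 | (15-10)/15 = 33% cut |
| CrCl ≥60, strong inhibitor | min(15, 10) = 10 | 10 | (10-10)/10 = 0% |
| CrCl 15-59, strong inhibitor | min(10, 10) = 10 | 5 | (10-5)/10 = 50% cut |

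The empty step is confined to the middle row. At 20,000-34,999 the CrCl ≥60 patient on an inhibitor goes to 5 mg, which is a real cut.

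**Step 2: starting count of 35,000-49,999 from disease, CrCl ≥60, strong inhibitor.**

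- The cap does not apply, because platelets are below 50,000.
- Level -1 does not apply, because a count taken before the first dose cannot be secondary to ruxolitinib.
- What remains is the starting dose: 15 mg twice daily, or 30 mg a day.
- The same patient at 50,000 or above gets 10 mg twice daily, or 20 mg a day.
- The background advice would give about 0.5 × 30 = 15 mg a day at either count.

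At CrCl 15-59 the starting dose is 10 mg at any count, so this gap does not arise there.

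**Step 3: rough scale in exposure terms.** Assume that the advised reduction r makes exposure equal with and without an inhibitor. The documents say approximately 50%; a range of 40-60% is taken. The equivalent dose without an inhibitor is D/(1-r).

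| Dose D on inhibitor | r = 40% | r = 50% | r = 60% |
|---|---|---|---|
| 15 mg | 25.0 | 30.0 | 37.5 |
| 10 mg | 16.7 | 20.0 | 25.0 |
| 5 mg | 8.3 | 10.0 | 12.5 |

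At the empty step, the 10 mg dose corresponds to 20/10 = 2.0 times (1.7 to 2.5) what a patient without an inhibitor receives at that count. Part of this comes from the size of the cap and not from the missing step: before any platelet fall the ratio is already 20/15 = 1.33. A 5 mg step would bring it to 10/10 = 1.0 (0.83 to 1.25).

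**The case against.** **Level -1 as a relative step.** An investigator might read the word reduction as one step below the current dose, which would give 5 mg. The table does not say so. Its levels are fixed doses, and where the plan means a relative step it says so, as in the row below 20,000 and the tables for nausea, vomiting and diarrhea. The general discretion clause cannot fill the gap, since it excludes thrombocytopenia.

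**The protocol is not silent below 50,000.** This has weight. Section 1.2.3 advises a reduction of about half at any count, and the Principal Investigator is to be told of each such patient. A reader might infer that the protocol orders an overdose, since 15 mg with an inhibitor could correspond to 30 mg (25 to 37.5) against the healthy-volunteer maximum tolerated dose of 25 mg twice daily in Section 1.2.2. The documents do not support that. The figure supposes that everyone disregards Section 1.2.3, and it treats an approximate dosing recommendation as a measured exposure ratio. What stands is that the operative dosing sections are narrower than the background and should be brought into line with it.

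**Safeguards.** Strong inhibitors are discouraged. Blood counts are done at least every 72 hours in weeks 1-5 (Section 12.2), the next band down goes to 5 mg without an attribution test, counts below 20,000 mean a hold, and Section 3.4.1 lets the investigator stop treatment for safety. These limit the harm. They do not supply a reduced dose at 35,000-49,999.

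**Resumption after a hold.** A reader might also see a conflict between the row below 20,000, which resumes one level lower, and the Level 1 row at 50,000-100,000. The specific instruction naturally governs, so this is not part of the point.

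**Conclusion.** The point holds in a limited form. For CrCl ≥60 on a strong CYP3A4 inhibitor, an attributed count of 35,000-49,999 brings a 0 mg reduction, where other patients get 5 mg. The cap's platelet condition also leaves a patient who starts in that band from disease at 15 mg under Sections 6.2 and 7, which is 5 mg per dose more than at 50,000 or above. Both results follow from the literal text and need no assumption. The exposure ratios do need one, namely that the advised reduction of about 50% matches exposure, and they serve only to show scale.

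No frequency can be given. The documents do not report how many patients will take strong inhibitors, how many will have CrCl ≥60, or how often an attributed fall into this band will follow a capped start. A reader might take the 36.9% in Section 8.1 as such a rate. It is a rate of reduction or interruption in myelofibrosis, is not specific to this band, and is put down there to protocol-mandated rules.

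This is a minor dosing-safety correction. It does not affect the sample size, the primary endpoint or the primary analysis.

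**What to change.** In Section 6.2, delete the platelet condition, so that 10 mg twice daily is the maximum at every count while a strong CYP3A4 inhibitor is taken. Add a note in Section 7 that this cap also limits the Level 1 row.

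In Section 7, add for patients with CrCl ≥60 on a strong CYP3A4 inhibitor:

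- At 35,000-49,999 attributed to ruxolitinib, give 5 mg twice daily.
- At 20,000-34,999, give 5 mg twice daily, or hold if the patient is already on 5 mg twice daily and the fall is attributed to ruxolitinib.

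The hold is needed because a 5 mg first step would otherwise move the empty step down to the next band. Tying it to attribution avoids stopping the drug for disease-driven counts. The tablet strength is 5 mg (Section 10.1.1), so the dose can be given.

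The cost is a few sentences by amendment, with no added procedures or patients. The downside is slightly lower exposure in a small subgroup of a lethal disease. If the 50% figure holds, the capped 10 mg start corresponds to about 20 mg and the 5 mg step to about 10 mg, neither below what patients without an inhibitor get at the same point (15 and 10 mg). If the true figure is 40%, the 5 mg step would be (10-8.3)/10, or about 17%, lower.
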